4.7.1.4 Vital signs / weight

Absolute values as well as absolute and relative changes from baseline for vital signs (systolic and diastolic blood pressure, pulse) and body weight, BMI, and BMI SDS will be presented by visit. Vital signs will be listed by center, patient number and visit and will include examination date/day, sitting pulse, and systolic and diastolic blood pressure.

4.7.1.5 Physical examination

The number and percentage of patients with significant findings will be summarized for each body system by visit for all non-missing patient evaluation data. Results of physical examination will be listed by center, patient number and visit and will include: examination date/day, weight, height, pubertal status, body system and if significant findings were identified, and if significant findings for other body systems were documented, specification will be given.

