2.3.2 Secondary Endpoints

2.3.2.1 Safety endpoints

Criteria for assessing long term safety of GH treatment focusing on the secondary objectives are:

- **Immunogenicity:** Number and percentage of patients developing anti-rhGH antibodies through the follow-up period after end of GH treatment is the secondary safety endpoint associated with monitoring and assessing immunogenicity.

Patients will be screened for anti-rhGH antibodies at baseline and 6 months after the end of treatment. Only in case of positive antibodies measurements in previous visit follow-up measurements are planned after 1 year, 5 years and 10 years. Positive antibodies are defined as values above 1.76. Unscheduled visits will be excluded from the analysis.

- **Laboratory evaluations – safety parameters:** Change from baseline (Shift from baseline, as applicable) at 6 months, 1 year, 5 years and 10 years after end of GH treatment in laboratory safety parameters as follows:
 - **Hematology:** Hemoglobin, hematocrit, white blood cell count (WBC, total and differential), red blood cell count (RBC), platelet count, mean cell volume (MCV), mean cell hemoglobin (MCH), mean cell hemoglobin concentration (MCHC), erythrocyte sedimentation rate (ESR).
 - **Biochemistry:** Creatinine, urea, aspartate aminotransferase (AST), alanine aminotransferase (ALT), gamma-glutamyltransferase (gamma-GT), alkaline phosphatase, total bilirubin, albumin, total protein, HDL, LDL, sodium, potassium, chloride, uric acid, fasting total cholesterol, fasting triglycerides, calcium, phosphorus.
 - **Thyroid function:** Free thyroxine and thyroid stimulating hormone.
 - **Urinalysis:** pH, glucose, ketones, bilirubin, protein.

- Number and percentage of patients with Adverse Events and Serious Adverse Events
- Change from baseline in vital signs parameters (blood pressure, pulse rate) and body weight, BMI, and BMI SDS will be assessed at each visit (baseline, 6 months, 1, 5, and 10 years after termination of treatment). BMI is calculated by [weight in kg] divided by [height in m]². For further details on the calculation of BMI SDS, see Section 5.1.
- Number and percentage of patients with significant finding in any body systems: head (external), eyes, ears, nose and throat, lungs, cardiovascular system, abdomen, musculo-skeletal system, skin, lymph nodes, central nervous system, and where appropriate, others. Physical examinations are performed at baseline, 6 months, 1 year, 5 and 10 years after end of treatment.

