4.1 General considerations

Data transfer from EP00-401

Some information for analyses planned in the protocol is not provided in the CRF of this follow-up study, but in the CRF of study EP00-401 only. Therefore, the following variables provided in the CRF of EP00-401 will be transferred to this study:

- age at final visit
- gender and race
- physical examination and pubertal status at final visit
- height, height Standard Deviation Score (SDS) at final visit
- weight and BMI, BMI SDS at final visit
- fasting plasma glucose, OGTT results, fasting plasma insulin, HbA_{1C} at final visit
- IGF-I, IGFBP-3, IGF-1 SDS, and IGFBP-3 SDS at final visit
- anti-rhGH antibody testing at final visit
- safety lab at final visit
- blood pressure and pulse at final visit
- exposure to study drug

Data of study EP00-401 will be transferred to EP00-402 on the same date the EP00-402 database is locked. In general, analysis data (i.e. data created for the analysis of EP00-401) will be transferred not the original CRF data.

Study days, baseline and visits

Study days are defined as date of assessment minus date of baseline visit.

Baseline is defined as final visit of study EP00-401. If no date of final visit is available, the date of F0 baseline visit of study EP00-402 will be used instead.

Analyses by visits will be based on CRF visits, i.e. F1 Month 6, F2 1 Year, F3 5 Years, and F4 10 Years/Final. The CRF visit F4 10 Years/Final will be presented as EOS (termination visit).

Conversion factors for laboratory parameters

In order to harmonize laboratory results by using the same units, some laboratory results will be converted. Corresponding conversion factors will be listed by parameter and will provide CRF unit, SI unit and conversion factor. If albumin is given in %, the respective values will be converted to g/l using total protein values.

[figure not shown]

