4.7.1.2 Safety parameters - Laboratory evaluations

Change from baseline (Shift from baseline) in hematology, biochemistry, thyroid function, and urinalysis parameters will be displayed by visit using descriptive statistics and/ or frequency tables depending on the type of variable (continuous or discrete).

4.7.1.3 (Serious) Adverse events

AEs are coded according to Novartis MedDRA, Version 19.1 or higher.

Only adverse event starting or worsening during study EP00-402 will be presented. Adverse events with missing or incomplete start dates not clearly attributable as starting/worsening prior to study EP00-402 will be included in the analysis.

A general summary table of AEs will contain the total number of AEs, the total number of SAEs, and separate descriptions of the splits for the variables relationship to study drug, action taken, outcome and intensity.

The incidence of an AE is defined as the number of patients who experience that event, divided by the number of patients in the SAF population. With AE incidence, each event will be counted only once for a given patient. More specifically, if a patient reports the same event more than

once, as determined by preferred term and system organ class, that patient will be counted only once for the incidence of the AE. For example, when a patient reported three instances of headache, this patient counts only once towards the total incidence of headache. Incidence of events within a system organ class is defined similarly. Whenever incidence is cross-tabulated with intensity in the summary tables, the incidence of an AE will be calculated for each level of intensity, i.e., the number of patients who experience that AE on a certain level of intensity.

The occurrence of an AE is defined as the total number of times the event occurs in the SAF population. With AE occurrence, a patient may contribute more than once to the total occurrence count. More specifically, if a patient reports a particular event, as determined by preferred term and system organ class (and having removed duplicate reporting of the same event) more than once, each event will count once towards the total event occurrence. Using the above example, headache would be counted three times for the patient who reported three separate occurrences of headache.

Occurrence tables will provide information about rates of AEs per patient-year, calculated as $12 \times \{(\text{number of events}) / (\text{months of study exposure})\}$.

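### The physical examination table gives only by-visit prevalence per body system, so it cannot separate findings present at baseline from those arising afterwards

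*SAP*

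**What the plan says.** SAP section 2.3.2.1 lists the physical examination among the criteria for long-term safety. The endpoint is "Number and percentage of patients with significant finding in any body systems", and the schedule reads "Physical examinations are performed at baseline, 6 months, 1 year, 5 and 10 years after end of treatment".

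Section 4.7.1.5 carries this out with one table: "The number and percentage of patients with significant findings will be summarized for each body system by visit for all non-missing patient evaluation data". It adds a patient-level listing: "Results of physical examination will be listed by center, patient number and visit". The listing shows the body system and whether a significant finding was identified. A written specification is mentioned only for findings in other body systems.

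Section 4.1 fixes the reference point: "Baseline is defined as final visit of study EP00-401". Its list of data to be transferred from the earlier study includes "physical examination and pubertal status at final visit".

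Other safety data are treated differently. Section 4.7.1.2 plans "Change from baseline (Shift from baseline) in hematology, biochemistry, thyroid function, and urinalysis parameters". Section 4.7.1.4 plans absolute and relative changes from baseline for blood pressure, pulse, weight, BMI and BMI SDS. Section 4.7.1.3 restricts the AE tables to events that began or worsened in EP00-402.

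**The concern.** For a safety follow-up after growth hormone, the useful question about the examination is how many patients acquired a finding that they did not have when treatment ended. A by-visit percentage does not answer it. A long-standing finding is counted again at each visit where it is recorded. A new finding in one patient can be offset by a resolved finding in another, or by the absence of a patient with an old one. The percentage can stay flat while new findings arise.

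The set of patients behind each percentage can also change. Section 2.1 says that the sponsor terminated the study and that all patients were called in for a last visit. Section 4.1 presents the 10-year/final CRF visit as EOS. A patient whose follow-up ended before five years would have no 5-year examination, and EOS can pool patients with different lengths of follow-up.

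At stake is how informative one descriptive secondary safety display is. In a study whose results are descriptive, the tables are the result, so this has some weight.

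**Working it through.** The SAP gives no rate for examination findings, so there is no figure to reproduce. The check has two parts.

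**1. The text, side by side**

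| Data | Baseline available | Planned use of baseline |
|---|---|---|
| Laboratory (4.7.1.2) | yes, transferred | change or shift from baseline |
| Vital signs, weight, BMI (4.7.1.4) | yes, transferred | absolute and relative change |
| Adverse events (4.7.1.3) | onset relative to baseline | only events new or worse in EP00-402 |
| Physical examination (4.7.1.5) | yes, transferred | none stated |

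The data for a within-patient comparison are therefore in the analysis database, and the planned table does not use them.

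**2. What by-visit prevalence can and cannot identify**

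Let pB be the proportion with a finding in one body system at baseline and pV the proportion at a later visit, in the same patients. The proportion with a finding at the visit but not at baseline lies between

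- lower bound: max(0, pV − pB)
- upper bound: min(pV, 1 − pB)

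All values below are assumed.

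- pB = 10%, pV = 10%: lower bound max(0, 0) = 0%, upper bound min(10%, 90%) = 10%. A flat table fits anything from no new finding to a complete turnover of affected patients.
- pB = 5%, pV = 10%: lower bound 10% − 5% = 5%, upper bound min(10%, 95%) = 10%.

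The bounds need the same patients at both times. If attendance changes, the baseline percentage no longer describes those attending. For example, 10/100 = 10% at baseline and 5/50 = 10% later fits 0 new findings (five old ones persist) up to 5 new findings (5/50 = 10% of those examined).

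So even a table that shows baseline beside each follow-up visit does not determine the number of new findings. A cross-classification within patients does.

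**The case against.** Four objections carry weight.

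- **The AE tables.** A reader might infer that new findings after treatment are never counted. The SAP does not support that. A new finding reported as an adverse event enters tables limited to events that began or worsened in EP00-402, and the AE listing flags onset or worsening on or after baseline (section 4.7.1.3). The SAP does not say whether every new significant finding must be reported as an adverse event. The protocol may, and it is not at hand, so neither answer can be assumed.
- **The listing.** It shows each patient's body-system result at each visit, so changes at system level can be traced. This stands, but the reader would have to derive the count by hand.
- **No contradiction.** Section 2.3.2.1 words the laboratory and vital-sign endpoints as change from baseline, but not this one, and section 4.7.1.5 implements the endpoint as worded. Tanner stage (4.4.2) and antibody status (4.7.1.1) are also shown by visit without a shift. This stands: the point concerns how informative the table is.
- **The size of any distortion.** One could argue that the percentage might double with no new finding: if all 10 affected patients out of 100 are among 50 later attenders, the table shows 10/50 = 20%. The arithmetic is right, but the case is extreme. With attendance unrelated to findings, its probability is C(90,40)/C(100,50), about 0.0006. Nothing in the SAP suggests such selective attendance, and section 4.2 reports how many patients are at each visit. The example should not be used to show the size of the problem.

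**Conclusion.** The point holds as a minor one. The only planned physical examination table is prevalence per body system and visit among those examined. It cannot separate pre-existing from newly arising findings, although the baseline examination is available and other safety data are compared with baseline. With 10% at both times in the same patients, the share with a new finding is undetermined between 0% and 10%. These percentages are assumed, because the SAP gives none.

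The documents do not support calling this an inconsistency or a loss of all information on new findings. No effect on the primary diabetes endpoint arises, and no study conclusion is shown to change.

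**What to change.** Keep the table and listing in section 4.7.1.5 and add two summaries:

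1. Per body system and follow-up visit, a shift from baseline with four cells (no/no, no/yes, yes/no, yes/yes), among patients with both a baseline examination and an examination at that visit.
2. Per body system, the count and percentage of patients with a significant finding at any follow-up visit. The denominator is patients with no significant finding in that system at baseline and at least one follow-up examination.

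Both should be defined at body-system level, because the only structured result that section 4.7.1.5 describes is whether significant findings were identified in a body system. A denominator based on the individual finding would need detail that the section does not describe.

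The cost is a few lines of SAP text and further tables from data already transferred. There are two limits. Patients without a baseline examination drop out of the added summaries but stay in the planned table. A second, different finding in an already affected body system still reads yes/yes, so the AE tables remain the place to see it if it was reported as an event.

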4.7.2 Efficacy evaluations

4.7.2.1 IGF-I and IGFBP-3 serum levels

The effect of treatment on serum IGF-I, IGF-I SDS, IGFBP-3 and IGFBP-3 SDS levels will be evaluated using descriptive statistics for the observed values at each visit together with the absolute and relative changes as compared to baseline.

4.7.2.2 Height measurements

The effect of treatment on height and height SDS will be evaluated by presenting absolute values for the observed values of height and height SDS at each visit. The effect of treatment on final height and final height SDS will be evaluated by presenting descriptive statistics for absolute values as well as absolute and relative changes from baseline of final height and final height SDS. The descriptive statistics for final height and final height SDS will only be calculated for the following patients:

- patients who completed study EP00-401
- females who discontinued study EP00-401 prematurely and are at least 16 years old when assessing final height
- males who discontinued study EP00-401 prematurely and are at least 18 years old when assessing final height.

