2.3.2.2 Efficacy Endpoints

Secondary efficacy endpoints of this study include:

- **Pharmacodynamic endpoints** Change from baseline in hGH-induced serum IGF-I and serum IGFBP-3 levels, as well as the respective serum IGF-I level SDS and serum IGFBP-3 level SDS, at 6 months, 1, 5 and 10 years after the end of treatment. For further details on the calculation/derivation of the serum IGF-I level SDS and the serum IGFBP-3 level SDS, see Section 5.3.
- **Height measurement related endpoints** include height, height SDS, final height, and final height SDS. Height will be measured according to the usual clinical practice at all visits including baseline, 6 months, 1, 5, and 10 years after the end of treatment. Height SDS will be calculated/derived from the height measurement for all visits including baseline, 6 months, 1, 5, and 10 years after the end of treatment. For further details on the calculation/derivation of height SDS, see Section 5.2. The final height is defined as the respective maximum value of height. Final height SDS is the respective SDS value for maximum value of height. For further details on the calculation/derivation of final height and final height SDS, Section 5.2.

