4.8 Handling of missing data in the analyses

IGF-1 and IGFBP-3 serum levels which are found to be below the level of detection will be imputed as one-half of the lower limit of detection for the corresponding analysis.

If for any laboratory parameter (hematology, blood chemistry, thyroid) a < or > sign is documented, this sign will be listed only. For calculation of summary tables, the respective value without sign will be used.

For safety or other efficacy parameters, missing values will not be imputed.

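### By-visit height SDS is summarised without the paired change from baseline planned for the other repeated measures; only final height gets one

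*SAP*

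**What the plan says.** Section 2.3.2.2 says that the height endpoints "include height, height SDS, final height, and final height SDS", so height SDS and final height SDS are separate endpoints. It adds: "Height SDS will be calculated/derived from the height measurement for all visits including baseline", followed by the 6-month, 1-year, 5-year and 10-year visits.

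Section 4.7.2.2 treats the two kinds of endpoint differently:
- The effect of treatment on by-visit height and height SDS "will be evaluated by presenting absolute values for the observed values of height and height SDS at each visit".
- Final height and final height SDS get absolute values "as well as absolute and relative changes from baseline of final height and final height SDS". This comes with a restriction: "The descriptive statistics for final height and final height SDS will only be calculated for the following patients". The list covers EP00-401 completers, and early discontinuers aged at least 16 (females) or 18 (males) when final height is assessed.

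Section 2.3.2.2 fixes one final-height value per patient: "The final height is defined as the respective maximum value of height".

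Other repeated measures get more. Section 4.7.1.4 plans "Absolute values as well as absolute and relative changes from baseline for vital signs", and also for weight, BMI and BMI SDS, by visit. Sections 4.6.2 and 4.7.2.1 do the same for the carbohydrate measures and for IGF-I, IGFBP-3 and their SDS.

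On missing data, section 4.8 says: "For safety or other efficacy parameters, missing values will not be imputed".

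**The concern.** With observed values only, the course of height SDS after growth hormone is stopped has to be read by comparing means across visits. That comparison is within patients only if the same patients are measured each time, and three features of the plan make this uncertain:

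- Section 2.1 reports that the sponsor ended the study early. A patient who stopped treatment less than about 5 years before that date cannot have the 5-year visit.
- Under section 2.6 a patient can enter the analysis through an adverse event alone, and so have a baseline height but no follow-up height.
- Under section 4.8 no missing height is filled in.

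If the patients measured at a visit were shorter or taller at baseline than the others, the visit mean shifts even when no patient's height SDS has changed. A reader could take that shift for loss or gain of height SDS after treatment. Section 4.1 transfers height SDS from the EP00-401 final visit, so a paired summary can be made from data that the plan already collects.

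**Working it through.** The SAP states no sample size, attendance figure or numerical result on this point, so there is no figure of its own to reproduce. The check has two parts.

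**1. Which measures have a paired by-visit summary**

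| Measure | SAP section | Change from baseline by visit |
|---|---|---|
| Glucose, OGTT, insulin, HbA1c, HOMA, QUICKI | 4.6.2 | yes |
| Blood pressure, pulse, weight, BMI, BMI SDS | 4.7.1.4 | yes |
| IGF-I, IGFBP-3 and their SDS | 4.7.2.1 | yes |
| Height, height SDS | 4.7.2.2 | no |
| Final height, final height SDS | 4.7.2.2 | one change per patient, not by visit, listed subset |

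Section 3 (changes to planned analyses) gives no reason for treating height differently.

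**2. Size of the possible artefact**

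Let p be the share of patients measured at a visit, m1 their baseline mean height SDS, m0 the baseline mean of those not measured, delta = m1 - m0, and c the mean within-patient change in those measured.

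- Visit mean = m1 + c
- Baseline mean of all patients = p x m1 + (1 - p) x m0
- Difference = c + (1 - p) x delta

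The second term is composition alone. Neither p nor delta is in the SAP, so the values below are assumptions (in SDS):

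| p | delta = 0 | delta = 0.2 | delta = 0.5 |
|---|---|---|---|
| 0.9 | 0 | 0.02 | 0.05 |
| 0.7 | 0 | 0.06 | 0.15 |
| 0.5 | 0 | 0.10 | 0.25 |
| 0.3 | 0 | 0.14 | 0.35 |

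For example, (1 - 0.3) x 0.5 = 0.35. A negative delta gives the same sizes with the sign reversed.

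A simulation with zero true mean change agrees with the identity. It assumed 200 patients, a baseline mean of -1.5, a between-patient SD of 0.8, random within-patient variation with SD 0.2, and nominal attendance of 0.8, 0.5 or 0.3.

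- Attendance unrelated to height SDS: the unpaired difference averaged 0.00. Its SD over repetitions was 0.03 to 0.09, against 0.02 to 0.03 for the paired change.
- Attendance more likely in shorter patients: the unpaired difference averaged -0.08 to -0.45. The far end implies a |delta| of at least 0.446 / 0.7 = 0.64, which lies outside the range in the table.
- The paired change averaged 0.00 in every scenario.

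**The case against.** The strongest reply is that the plan already pairs the height measure that matters. The secondary objective in section 2.2 names final height, and section 4.7.2.2 plans its change from baseline. The listed subset leaves out only early discontinuers below the age limits. Section 2.3.2.2 defines the height endpoints without the words for change that it uses for IGF, so the analysis matches its endpoint and nothing is contradicted. This stands as far as it goes: a reader might infer that height SDS is never compared within patients, and that is not so.

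It does not close the gap. Final height is a single maximum per patient and gives no paired change at 6 months, 1 year or 5 years. Under section 5.2 its SDS uses reference values for 18 years or older, whereas height SDS in general uses chronological age. For a completer who is still younger, the change can therefore mix two reference ages.

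Four further points stand:
- A reader might infer that changing attendance does bias the visit means. The SAP does not show this: it gives no attendance figures, and a calendar cut-off need not be related to height SDS. If it is not, the result is extra noise and no systematic shift.
- All patients were called in at termination (section 2.1), and that visit is shown as EOS (section 4.1). The calendar argument therefore concerns the 5-year visit, not EOS.
- Summary tables show valid and missing counts (section 2.1), and height is listed by patient and visit (section 4.7.1.5). Attrition is thus visible, but the tables do not show whether those measured differed at baseline.
- Section 4.1 says that baseline height SDS will be transferred, not that it is complete. It cannot be assumed available for every patient.

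**Conclusion.** The point holds in a limited form. By-visit height and height SDS lack the paired change that the plan gives to its other repeated measures, and the final-height change does not supply it. A difference between visit means could therefore partly reflect who was measured.

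The distortion is zero if attendance is unrelated to baseline height SDS. It is at most about 0.35 SDS in either direction under p of 0.3 to 0.9 and |delta| of 0 to 0.5, all of which are assumptions. The documents do not support the stronger reading that such a distortion is present or that its direction is known.

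Severity is minor: this is a descriptive secondary display in a safety study whose primary endpoint is diabetes, and no inference rests on it.

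**What to change.** In section 4.7.2.2, add absolute change from baseline in height SDS and in height at each visit, calculated in patients with both a baseline and a visit value. Beside it, show the number of such patients and their own baseline mean. The paired change removes the (1 - p) x delta term. The baseline means show whether the group measured has shifted from visit to visit.

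The cost is one sentence in the SAP and a few columns in an existing table. It needs no new data, imputation or change to the final-height analysis. Patients without a transferred baseline value drop out of the paired columns, and the count shows how many.

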2.1 Study documents and general considerations

This document describes the procedures and conventions to be used in the final analyses with data of all patients who were included into study EP00-402.

The study is based on the

- study protocol V 1.0, dated 16 Mar 2007,
- Amendment no. 01, dated 12 Mar 2012 incorporated into protocol v 1.0 leading to protocol v 2.0, dated 12 Mar 2012,
- Amendment no. 02, dated 9 May 2012 incorporated into protocol v2.0 leading to protocol v3.0, dated 9 May 2012,
- Amendment no. 03, dated 6 Jun 2013 incorporated into protocol v3.0 leading to protocol v 4.0, dated 6 Jun 2013,
- Amendment no. 04, dated 14 July 2014 incorporated into protocol v4.0 leading to protocol v5.0, dated 14 July 2014.

This study was terminated by the sponsor [REDACTED] Following decision of [REDACTED] study termination all patients were called in for a last visit (documented on the final visit page of the case report form (CRF)).

Raw data listings, summary tables, graphs and statistical tests will be generated by means of the program SAS 9.3 or higher.

The following descriptive statistical parameters will be shown in summary tables

- Continuous variables: n (valid cases), n (missing data), mean, median, standard deviation (SD), min, max, quartiles
- Categorical variables: Count and percentage of category. Percentages are routinely based on the total category count excluding the missing category if not otherwise mentioned. Percentages showing a rate relative to the total number of patients in this group are given in special tables (e.g. Adverse Event (AE) tables). Footnotes will specify the percent basis.

For continuous variables, if not otherwise specified, mean, median and quartiles will be reported to one decimal place greater than the precision of data as collected. Standard deviation will be

presented in two decimal place greater than the data and minimum/ maximum values will be reported with the same precision, as they were collected. This rule is only valid if values are not converted for the summary.

Generally, percentages will be displayed in the format xx.d, i.e. one decimal place will be shown; if the calculated percentage is 100, no decimal is required (i.e. 100% and not 100.0%). If the count is zero no percentage needs to be shown.

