5.1 BMI SDS

As the probability distribution of the BMI is skewed, a satisfying description of the BMI needs additional characterization of the skewness. This is usually done by the LMS method (Cole and Green 1992). If the same reference for height and weight also included BMI reference values they were used. If the reference for height and weight does not include BMI reference values they were appropriately derived from height and weight.

The following references for the calculation of BMI SDS will be used in each country:

Country	Literature reference

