5.2 Height SDS

Standard Deviation Scores (SDS) are the relative deviation from the mean value of normally growing children of same gender and chronological age. In general, the SDS values for height will be calculated according to the following formula $SDS = (X1 - X2) / SD$, where X1 means the measured value, X2 the mean value for the relevant chronological age and gender, and SD the standard deviation for the relevant chronological age and gender applying the references as outlined below. If respective national references are provided as median and 3rd percentiles SDS values will be calculated according to the following formula: $SDS = (X1 - X3) / (0.5 * (X3 - X4))$, where X1 means the measured value, X3 the median value for the relevant chronological age and gender, and X4 the 3rd percentile for the relevant chronological age and gender applying the references as outlines below. Resulting SDS values will be rounded to two digits. In case age is higher than maximum age in the respective reference, maximal age will be used for the calculation.

Standardization of patients' height will be performed using the following national reference:

Country	Calculation	Literature reference

To derive reference values for age groups in between the age groups reported in literature, the original tables were extended by linear interpolation between the reported values for mean and standard deviation. Final height SDS will be calculated according to national reference ranges (using the reference values for 18 year olds or older age if available).

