5.3 IGF-1 and IGFBP-3 SDS

Standardization of patients' IGF-1 and IGFBP-3 will be performed according to Elmlinger (2004). SDS values will be assessed according to the following formulas: $SDS = (X1 - X2) / ((X2 - X3) / 2)$ if $X1 < X2$ and $SDS = (X1 - X2) / ((X4 - X2) / 2)$ if $X1 \geq X2$, where X1 means the measured value, X2 the mean value for the relevant chronological age and gender, X3 the -2 SD value for the relevant chronological age and gender, and X4 the +2 SD value for the relevant chronological age and gender according to Elmlinger (2004).

Mean, -2 SD, and +2 SD values given by Elmlinger (2004) are provided for age intervals. These values were used as references for patients with an age equal to the mid of this age interval. For

patients with an age between two mids of age intervals, mean, -2 SD, and +2 SD values will be interpolated.

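### Relative change from baseline is planned for four standard deviation scores (final height, BMI, IGF-I, IGFBP-3), where a ratio to baseline has no meaning

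*SAP*

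**What the plan says.** Three sections of the SAP ask for relative as well as absolute change from baseline and include SDS variables:

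- Section 4.7.2.2, for final height and its score: "absolute and relative changes from baseline of final height and final height SDS".
- Section 4.7.1.4, where BMI SDS shares a sentence with blood pressure and weight: "absolute and relative changes from baseline for vital signs (systolic and diastolic blood pressure, pulse) and body weight, BMI, and BMI SDS".
- Section 4.7.2.1, for both IGF scores and the raw serum levels: "IGFBP-3 SDS levels will be evaluated using descriptive statistics for the observed values at each visit together with the absolute and relative changes".

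Height SDS by visit is to be shown as absolute values only (Section 4.7.2.2), so it is not affected.

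The scores are defined in Section 5. Section 5.2 explains that "Standard Deviation Scores (SDS) are the relative deviation from the mean value of normally growing children", gives the height formula as measured value minus reference mean, divided by the reference SD, and adds: "Resulting SDS values will be rounded to two digits". Section 5.3 has one IGF formula for values below the reference mean and another for values at or above it, with "X2 the mean value for the relevant chronological age and gender, X3 the -2 SD value" among its terms. Section 5.1 describes the skewness of BMI and says of it: "This is usually done by the LMS method".

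Section 2.1 lists the statistics for every continuous variable, including "mean, median, standard deviation (SD), min, max, quartiles". No section gives a formula for relative change, exempts the SDS variables, or says what to do with a zero baseline.

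**The concern.** Relative change needs a scale with a true zero. Height in cm, weight, BMI and serum concentrations have one. A standard deviation score does not: a score of 0 means that the child sits at the reference mean. A change expressed as a share of the baseline score therefore depends on where the child happened to lie relative to that mean, and not only on how much the child changed.

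Three problems follow:

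1. If the change is divided by the signed baseline, every negative baseline reverses the sign. A gain prints as a fall and a loss as a rise.
2. If the baseline is 0, the quantity does not exist. Height SDS is rounded to two digits, so exactly 0.00 can occur.
3. If baselines lie near 0, single patients produce very large percentages that dominate the mean, SD, minimum and maximum.

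The stake is a final height SDS table in which a gain, if there is one, from mostly negative baselines stands as a percentage fall next to a correct absolute gain. For IGF and BMI SDS, it is a mean percentage driven by a few patients.

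**Working it through.** The SAP states no figure to reproduce here. The check applies the ordinary definition to the SAP's own scores.

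**Formulas.** With baseline score b and follow-up score f:

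- signed version: R = 100 × (f − b) / b
- absolute-denominator version: R* = 100 × (f − b) / |b|

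The SAP states neither, but a relative change set beside an absolute change from baseline can hardly mean anything else.

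**Worked values, with no distribution assumed.**

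| b | f | f − b | R | R* |
|---|---|---|---|---|
| -3 | -2 | +1.0 | 100 × 1/(-3) = -33.3% | +33.3% |
| -2 | -1 | +1.0 | 100 × 1/(-2) = -50% | +50% |
| -0.5 | +0.5 | +1.0 | 100 × 1/(-0.5) = -200% | +200% |
| +0.5 | +1.5 | +1.0 | 100 × 1/0.5 = +200% | +200% |
| 0 | +1 | +1.0 | undefined | undefined |
| -1 | -2 | -1.0 | 100 × (-1)/(-1) = +100% | -100% |
| -0.1 | +0.2 | +0.3 | 100 × 0.3/(-0.1) = -300% | +300% |
| +0.1 | +0.4 | +0.3 | 100 × 0.3/0.1 = +300% | +300% |

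The first four rows are the same gain of 1.0 SDS. R runs from -200% to +200% and R* from 33.3% to 200%. The difference comes entirely from the starting point.

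**Illustration at table level.** The SAP gives no SDS distributions, so all inputs here are assumptions: n = 120 and 4000 simulated trials, with 95% ranges over trials.

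- *Final height SDS*, baseline mean -1.8 and SD 0.8, change +0.3 (SD 0.4), scores rounded to two digits. The absolute change is 0.30 (0.23 to 0.37). The median of R is -16% (-22 to -11) and is negative in 100% of trials. The mean of R ranges from -56% to +17%. The median of R* is +17% (12 to 22), but its mean ranges from 12% to 77%.
- *IGF or BMI SDS*, baseline mean +1 and SD 1, change -1.0 (SD 0.7), unrounded. The absolute change is -1.00 (-1.12 to -0.88). The median of R is -64% (-83 to -47), with the right sign. The mean of R ranges from -907% to +1078% and has the right sign in only 73% of trials. Its tails are so heavy that these limits move with the random seed; two other runs gave -1023% to +790% and -987% to +812%.
- *IGF or BMI SDS*, baseline mean 0 and SD 1, same change. The median of R runs from -50% to +50% and has the right sign in 50% of trials.

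**Chance of a zero height baseline.** For baseline mean -1 and SD 1, the normal density at 0 is 0.242, so a score rounds to 0.00 with probability 0.01 × 0.242 = 0.00242. Among 120 patients, at least one does so with probability 1 − (1 − 0.00242)^120 = 25%. For mean -1.8 and SD 0.8, the simulated share of trials is 5%.

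**The case against.** The strongest case on the other side has four parts.

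- **The sign error is not written into the SAP.** It says relative and gives no denominator. A programmer could divide by |b|, which restores the sign and gives a stable median in these scenarios. This is fair. What holds under either denominator is narrower: the arbitrary zero, the missing value at 0, and the unstable mean and SD.
- **Negative height baselines and a later gain are assumed.** The introduction says that the children were treated for short stature, but baseline here is the final visit of EP00-401 (Section 4.1), after treatment. Negative scores remain plausible, but how far below zero they lie is not given. With a mean change of zero and the same baseline (mean -1.8, SD 0.8), the median of R is 0% (-5 to +5) and the summary shows no reversal. The sign reversal is therefore conditional on the change that occurs; it is not a prediction for this table.
- **Median and quartiles are planned too, and resist outliers.** True, but they do not repair the scale. Under the signed formula the median of the first height scenario has the wrong sign.
- **Nothing rests on these columns.** Section 2.4 makes the summaries descriptive, and absolute values and changes appear alongside. This stands, and it limits the point to a minor one.

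None of this makes the percentage meaningful.

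**Conclusion.** The point holds and is minor. That relative change is planned for four scores without a true zero follows from the SAP's text and definitions and needs no assumption; nor does the undefined value at a zero baseline. The wrong sign depends on a signed denominator and negative baselines. The simulated sizes depend on assumed means, SDs and sample size; they show the kind of distortion to expect and are not forecasts for this trial. The primary diabetes endpoint, the absolute changes and height SDS by visit are not affected.

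**What to change.** In Sections 4.7.1.4, 4.7.2.1 and 4.7.2.2, delete relative change for BMI SDS, IGF-I SDS, IGFBP-3 SDS and final height SDS, and report these four as observed values and absolute change only. Keep relative change for the ratio-scale variables in the same sections: blood pressure, pulse, body weight, BMI, serum IGF-I, serum IGFBP-3 and final height in cm.

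The cost is a wording change in three sections and the removal of four sets of table columns. No further data are needed. No endpoint is lost: Sections 2.3.2.1 and 2.3.2.2 define the BMI SDS and IGF SDS endpoints simply as change from baseline, which absolute change satisfies, and final height SDS as a value.
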